 - ii. If they do not answer, GRA will leave the voicemail and record the date and time of the missed call
 - iii. Third attempt will be email to set up a time to return call

The following script will be the check in call questions read to the participants.

Hi, my name is _____, and I am a researcher on the Step Away project. I'm calling to ask a few questions about how your experience participating in the Step Away study has been going. Do you have a few minutes?

Great. Thanks for taking the time to answer a few questions.

If they have downloaded:

Glad to see you have had the chance to download the app! How has the program been working for you?

Have you encountered any glitches?

Probe: Was there a time when you used the app and it didn't work the way you expected?

What happened?

Provide tech assistance here if necessary.

If they haven't downloaded:

It looks like we emailed you instructions for downloading the app on [date] but does not look like you have downloaded it yet.

Did you receive the instructions?

If no: Sorry to hear that. I'll resend the instructions right now. Please check your spam as well in case it sent there.

Have you had any challenges setting up the app?

Assist with any challenges over the phone if possible and help them download the app.

If not possible over this call: I will have someone contact you at this number shortly to help walk you through how to fix this glitch.

If you encounter any future glitches please contact us at

[contact].

Now I'm going to ask a few questions about your alcohol use over the past two weeks (so keep that timeframe in mind).

In the past two weeks, how often have you had a drink containing alcohol?

- (0) Never
- (1) Less than monthly
- (2) Monthly
- (3) Weekly
- (4) 2-3 times a week
- (5) 4-6 times a week
- (6) Daily

How many drinks containing alcohol do you have on a typical day when you are drinking?

- (0) 1
- (1) 2
- (2) 3
- (3) 4
- (4) 5-6
- (5) 7-9
- (6) 10 or more

How often do you have X or more drinks on one occasion? (5 for men under age 65; 4 for men aged 65 or older and all women)

- (0) Never
- (1) Less than monthly
- (2) Monthly
- (3) Weekly
- (4) 2-3 times a week
- (5) 4-6 times a week
- (6) Daily

Do you believe the Step Away app is causing you to drink more than you usually do?

Total AUDIT 1-3:

If 3 points above baseline:

It seems like you may benefit from further treatment. If you would like, I can connect you with some treatment centers in your area.

If yes: Do you have a few more minutes to stay on the line while I call for services in our area with you?

If yes: call [name] and begin warm handoff (ask them what state they are from)

Hi, my name is ____ and I'm a researcher on a current alcohol study. I have ____ (name of participant) here on the phone line with me and they are interested in finding services in ____ (their state). Can you help connect them?

If no: What email would you like me to send the resources to?
(findtreatment.gov/ or call [[name]]([contact]))

The last few questions are about how you have been feeling over the past two weeks.

1. How often have you been bothered by feeling down, depressed, or hopeless?
 - (0) Not at all
 - (1) Several days
 - (2) More than half the days
 - (3) Nearly every day
2. I am going to read some statements to you. Please tell me which statement best describes how you have been feeling over the past two weeks.
 - (0) I do not feel sad
 - (1) I feel sad
 - (2) I am sad all the time and I can't snap out of it
 - (3) I am so sad and unhappy that I can't stand it
3.
 - (0) I am not particularly discouraged about the future
 - (1) I feel discouraged about the future
 - (2) I feel I have nothing to look forward to
 - (3) I feel the future is hopeless and that things cannot improve

If 5 or higher:

Have the symptoms I just asked about gotten worse over the past two weeks?

If yes: Do you believe the Step Away app is contributing to your increased level of distress?

If yes: It sounds like this study is not a good fit for you. You may delete the app and discontinue using it. [*Continue with resources*].

All positives: Based on your answers you may benefit from discussing these issues further. I'm going to send you some phone numbers, where you can either text or call to talk to someone with experience discussing these issues.

Is that OK? (wait for response before moving on)

You may also text "MHA" to [name] to speak with a professional via text.

If you are feeling distressed and wish to talk over the phone, you may call the National Suicide Prevention Hotline at [name]. They also have a live online chat at suicidepreventionlifeline.org.

What email would you like me to send these resources to?

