An intervention for alcohol misuse problems, via the Step Away chatbot and the Step Away app will be provided at no charge to participants. The project will contribute information on a new method for delivering and/or enhancing tools for people who are seeking to reduce their alcohol use, especially to those who otherwise are unable or unwilling to seek traditional alcohol misuse treatments. We believe the combined direct therapeutic benefits to participants and the new scientific information to be gained in the proposed study clearly outweigh the risks involved.

Known Potential Risks

Potential harms for participants include:

- a. Confidentiality: potentially adverse effects if others learn that a participant is participating in an alcohol intervention.
- b. Stress: related to completing questionnaires and interviews of a sensitive nature. However, the information obtained will have clinical value in that the participant's treatment and the assessment procedures are similar to those typically used in clinical work.
- c. Exacerbation or worsening of alcohol intake or other psychiatric problems during the interventions. This may occur during the study with some participants but is a risk factor for all community treatment programs. All intervention systems will contain immediate access to help (suicide hotline, 911, military or veteran hotline if they indicate they are in the military or are a veteran and the phone number to the SAMHSA treatment helpline if the participant would like to find face-to-face intervention in their geographic area). There is the possibility that one of the apps will experience a crash during the study. Participants will be informed of this possibility upon signup and will be provided with the phone number for Here and Now Systems IT support to report the crash. They will also be given the phone numbers to the SAMHSA treatment helpline, suicide hotline and encouragement to call 911 if they are in an acute emergency and are unable to utilize one of the intervention systems.

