- The treatment history section of the Form 90 will be modified to be administered online at baseline and follow-up, to gather lifetime treatment history, self-help attendance, and treatment use.
- Readiness to Change. We will utilize the Readiness to Change Treatment Version (RCQTV), which RCQTV has been shown to have solid reliability and validity and has been modified for individuals contemplating or engaged in treatment for alcohol problems.

Follow-Up

The US AUDIT, TLFB, SIP-R, and Readiness to Change questionnaires will be used for the follow-up assessments. In addition, those in the app and chatbot groups will be asked to complete the System Usability Scale to assess their perceptions of the interventions' usability. The follow-up survey will be sent to participants at 4 months post-enrollment.

Interviews

Interviews will be conducted after the completion of the follow-up survey. Interview questionnaires will focus on users' experiences with the app or the chatbot. These interviews will be conducted over the phone.

8. Assessment of Safety

Several safety measures will be put in place to ensure the safety, comfort, and confidentiality of all participants. Care will be taken to inform potential participants fully before they consent to participate about all potential risks that may arise from their participation. The two most important aspects of participant protection in the proposed work are assuring the adequacy of informed consent (including full disclosure of all potential risks) and protecting confidentiality. To minimize risk, we will clearly explain all procedures to participants in our informed consent documents and clearly outline safeguards for confidentiality implemented in the study. Further, in order to protect their confidentiality, all participants will be encouraged to set a password to access their smartphone home screen.

Also, a Data Safety Monitoring Board (DSMB) will be convened in Year 1 of the project and will include the following two members with expertise in psychology, behavioral health, and

research ethics. The DSMB will meet twice during each year of the project to review the status of the project.

9. Statistical Considerations

All randomized study participants who complete both the baseline and follow-up surveys will be the primary population for the analysis. Three subgroups will be analyzed: the app group, the chatbot group, and the delay group.

Outcomes, Statistical Methods, and Statistical Analyses

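### The check-in script asks whether the app is making the participant drink more, but attaches no step to a yes and shows no route for recording it

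*Combined protocol and SAP*

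**What the plan says.** Section 3 of the protocol (Known Potential Risks, item c) puts two harms in one line: "Exacerbation or worsening of alcohol intake or other psychiatric problems during the interventions". The same section says that procedures for exacerbation have been developed and are described further on.

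The check-in call script in the appendix covers both harms.

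- **Drinking.** After three alcohol items the caller asks "Do you believe the Step Away app is causing you to drink more than you usually do". The next line is the total of the three items. The one conditional instruction that follows is headed "If 3 points above baseline", and its text is "It seems like you may benefit from further treatment. If you would like, I can connect you with some treatment centers in your area". The yes and no branches after that belong to the referral offer, not to the attribution question.
- **Mood.** After three mood items, a score of 5 or higher leads to "Have the symptoms I just asked about gotten worse over the past two weeks". A yes leads to "Do you believe the Step Away app is contributing to your increased level of distress". A further yes leads to "It sounds like this study is not a good fit for you. You may delete the app and discontinue using it", followed by a list of resources.

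On oversight, Section 8 (Assessment of Safety) says "The DSMB will meet twice during each year of the project to review the status of the project". Section 6 allows an investigator to end participation when an exclusion criterion is met.

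**The concern.** A participant who says that the intervention is making them drink more is reporting, in plain terms, the harm that the trial is meant to reduce. The script asks for that report and then does nothing with it. Because the script is meant to be read to participants, a caller who follows it exactly moves from a yes to adding up the score, and from there, if the score has not risen enough, to the mood items.

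The mood block shows that the authors thought an attribution answer should change what happens next. The drinking block lacks the equivalent step, although Section 3 treats the two harms as one risk.

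At stake is the trial's ability to detect and describe intervention-related harm. Section 3 relies on the absence of reported adverse events in previous studies of Step Away and its prototype. A similar statement about this trial would be hard to support if yes answers had been collected with no stated way of counting or reviewing them. The principal investigator's disclosed financial interest in the product's owner (Section 10, Conflict of Interest Policy) makes a written route to the separate overseeing investigator more useful.

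**Working it through.** The plan gives no figure to reproduce here. The check is a trace of the script, followed by arithmetic on its own scoring.

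**1. Does the attribution answer change anything in the drinking block?** I cross the answer with the change in the three-item total, reading the trigger as a rise of at least 3.

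| Blames the app for more drinking | Rise below 3 | Rise of 3 or more |
|---|---|---|
| Yes | No alcohol response; on to the mood items | Referral offer |
| No | No alcohol response; on to the mood items | Referral offer |

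The two rows are identical, so the answer alters no scripted step.

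**2. Does the score trigger catch the same people?** Each of the three items is scored 0 to 6. Take a participant who has 3 drinks per drinking day and never reaches the 4- or 5-drink occasion limit.

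- Drinking 2 to 3 times a week: frequency 4 + quantity 2 + heavy occasions 0 = 6.
- Drinking daily: frequency 6 + quantity 2 + heavy occasions 0 = 8.
- Change: 8 − 6 = 2, below the trigger.
- Weekly intake: from 2 × 3 = 6 up to 3 × 3 = 9 drinks, to 7 × 3 = 21 drinks.

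Intake has at least doubled (21 against 6 to 9) and the trigger does not fire.

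**3. Is there a ceiling?** The maximum total is 3 × 6 = 18, and 18 − 3 = 15. A participant with a baseline of 16, 17 or 18 can never rise by 3. Such totals are possible within the upper USAUDIT eligibility limit of 24 (Section 6), assuming that the baseline items use the same 0 to 6 options.

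**4. How does the mood block compare?** The mood attribution question is reached only with a score of at least 5 out of 3 × 3 = 9 and reported worsening. A yes then has its own instruction. The drinking question is put without either kind of prior condition, and a yes has none.

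**5. Where would a yes go?** I looked for a route in the rest of the visible text. Section 8 covers consent, confidentiality and the DSMB's two meetings a year. It does not define an adverse event, say who records a call answer, or say how one reaches the overseeing investigator, DSMB or IRB. The termination rule in Section 6 is tied to exclusion criteria, not to app-attributed worsening. The three-item total cannot by itself show the exclusion score of 25, since its maximum is 18.

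**The case against.** The strongest reply is that worsening drinking is acted on, by measurement instead of opinion: a 3-point rise brings a referral offer with a direct handoff or emailed resources, and Section 3 says that all the intervention systems give immediate access to help. That stands, and it rules out a reading that such participants get no action at all. It does not supply a consequence for the answer itself, and step 2 shows that a large increase in drinking can fall short of the trigger.

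Second, the mood contrast can be overdrawn. A reader might infer that a mood complaint simply leads to stopping the app. In fact two conditions come first, and the wording is permissive. The difference that remains is that one attribution answer has an instruction and the other has none.

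Third, a reader might infer that yes answers go unreported. The documents cannot show that. Parts of the appendix are not in the text available, including what comes immediately before the script, and they may hold instructions to callers. Only the absence of a visible route can be stated.

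Fourth, the resources step for all positive answers might be read as covering the drinking question. Its place at the end of the mood block and its crisis-line content make that unlikely.

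Finally, worsening drinking is one of three unranked harms in Section 3. The protocol reserves its strongest wording for confidentiality, so calling this the main harm has no support.

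**Conclusion.** The point holds in limited form. In the visible script, a yes to the drinking attribution question changes no step whatever the score, and with a rise below 3 points it meets no alcohol response. This is inconsistent with the mood block, with the joint naming of the two harms and with the procedures that Section 3 promises. No recording or escalation route is visible.

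Every yes is affected, but how many there would be is unknown: the documents give no expected rate and the script itself plans for missed calls, so I offer no count. The conclusion assumes that the script is followed as written and that the removed appendix text does not supply the missing step. If it does, the remaining task is to refer to it in the script. The change is worth making because it is cheap and concerns a direct report of harm.

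A smaller ambiguity sits beside this. The mood wording says that the study is a poor fit but instructs only on use of the app, so it is unclear whether the participant stays in follow-up. Section 9 limits the primary population to those who complete both surveys, so anyone who took it as leaving the study and skipped the 4-month survey would drop out of the main analysis. The text does not tell the participant to leave, and I do not claim that it does.

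**What to change.** - Reconcile Section 3 (item c and the promised exacerbation procedures), Section 8 and both blocks of the script, so that a yes to the drinking question has a stated next step. Its clinical content is for the investigator and IRB to decide.
- Log each yes to either attribution question as a possible intervention-related event, send it to the overseeing investigator when it occurs, and tabulate it by arm for the DSMB. Report with it the number of participants in each arm who were reached and asked, since the mood question is put only to some.
- Reconcile the mood wording so that it is clear whether stopping the app also means leaving the study.

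The cost is a few script lines, one logged field, an IRB amendment and a few more events to review. No extra calls are needed.

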The interventions offered in this protocol, although self-administered and delivered via a novel mechanism (smartphones), are consistent in terms of content with interventions for alcohol problems that have research evidence for efficacy (e.g., Relapse Prevention). Further, similar self-administered interventions delivered via smartphone, bibliotherapy and the internet have been shown to be effective in substantially reducing alcohol intake. We have developed procedures to deal with the potential issue of exacerbation associated with participation in this study (see below).

In all studies to date of Step Away (2 with U.S. Veterans and one in New Zealand) and its prototype, the LBMI-A (performed at UAA in 2012), no adverse events have been reported.

4. Study Objectives and Purpose

This project will finalize development of the Step Away chatbot, which has been in process for over a year, and create an improved user interface for the Step Away app. We will then conduct a pilot study that compares three conditions, both Step Away interventions (i.e., smartphone app and chatbot) and a wait-list control condition that will receive the app after a 3-month delay. The trial focus will be on determining if the Step Away chatbot has better user engagement with regard to improved utilization of the features, enhanced intervention fidelity and improved alcohol outcomes compared to the Step Away app. Qualitative interviewing of 10 participants in each intervention group will identify perceptions of each intervention's usability and potential barriers to utilization.

Specific aims:

1. Develop a chatbot version of Step Away that delivers the interventions through an interactive format, and that proactively introduces the intervention features in a texting-based, narrative framework.
2. Conduct a pilot randomized controlled trial with a sample of problem drinkers (N = 150) to identify and compare differences in utilization and alcohol outcome efficacy between the Step Away chatbot, the Step Away app and a wait-list control condition.

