A prescreen survey will be hosted through Qualtrics. It will survey for eligibility criteria which includes demographic questions and the US AUDIT screening questionnaire. Participants will be automatically directed to the consent form hosted on Qualtrics if they are eligible. They will automatically be directed to a debriefing screen and resources if they are not eligible. The AUDIT is the most widely used alcohol screening test in the world with more than 25 years of validation studies worldwide. We will use the USAUDIT, a recent adaptation of the original AUDIT that uses U.S. standard drink amounts and NIAAA drink limits. A score of 8 or greater on the USAUDIT suggests that they are at risk of experiencing significant problems from drinking alcohol. This cut point has been found to yield high sensitivity and specificity when compared to a number of criteria for problematic alcohol use (e.g., alcohol dependence); thus, numerous studies have found it to be an accurate screening tool for alcohol problems among numerous groups including women and older adults. In the current study, the standard cut point of 8 for men and 6 for women and men over 65 will be used to establish problem drinking. Participants with high likelihood of alcohol dependence, evidenced by a score of 25 or above will be screened out of the study.

Target Sample Size

The target sample size is a minimum of 50 participants per intervention arm (i.e., app group, chatbot group, delay group). This will provide adequate power to detect modest effect sizes, pre to post, in outcomes for pilot purposes. For the interviews, 20 participants (10 from the app group and 10 from the chatbot group) will be randomly selected and asked to participate.

Participant Withdrawal or Termination

Participants are free to withdraw from participation in the study at any time upon request. An investigator may terminate participation in the study if the participant meets an exclusion criterion (either newly developed or not previously recognized) that precludes further study participation.

7. Study Procedures and Schedule

This study will consist of three phases. Phase I will focus on developing the AI chatbot version of Step Away and developing procedures for the pilot study, including evaluating the different program elements using an expert panel.

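### In the visible check-in script, a participant whose mood has worsened but who totals 4 or less out of 9 is not asked about worsening or the app's role in it

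*Combined protocol and SAP*

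**What the plan says.** Section 3 (Known Potential Risks, item c) lists as a possible harm "Exacerbation or worsening of alcohol intake or other psychiatric problems during the interventions". It later adds: "We have developed procedures to deal with the potential issue of exacerbation associated with participation in this study (see below".

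The appendix contains a check-in call script. After the drinking questions it reads three mood items covering the past two weeks: frequency of low mood, sadness, and outlook on the future. Each has four options scored 0 to 3. The top option on the third is "I feel the future is hopeless and that things cannot improve".

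The next line restricts what follows to a score of 5 or higher. Below it come, in order:

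1. "Have the symptoms I just asked about gotten worse over the past two weeks"
2. If yes: "Do you believe the Step Away app is contributing to your increased level of distress"
3. If yes again, the participant is told that the study does not seem a good fit, and: "You may delete the app and discontinue using it"

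A separate line then introduces the mental-health resources: "All positives: Based on your answers you may benefit from discussing these issues further". The script does not define that label.

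**The concern.** The named risk is a change for the worse, but the script decides whom to ask about change by how bad things are now. A participant who began the study well and has slipped to moderate symptoms has worsened, yet may never be asked. The same holds for someone with a single severe answer and low answers elsewhere.

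What is at stake is participant safety. The advice that a participant may stop is the script's direct response to distress attributed to the app. At a total of 4 or less it cannot be reached. Sample size, power and the planned efficacy analysis do not depend on this branch.

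**Working it through.** **Inputs (appendix, check-in call script).** Three mood items, each scored 0 to 3. The gate is 5 or higher.

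**What the gate must mean.** The script does not say whether 5 is a total. One item can reach at most 3, which is below 5, so the gate can only be a sum. The maximum sum is 3 × 3 = 9. The gate is therefore a total of at least 5 out of 9.

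**Tracing participants through the script.** Scores are in the order low mood, sadness, outlook.

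| Answers | Total | Asked about worsening? | Can reach app-role question and stop-use advice? |
|---|---|---|---|
| 2, 1, 1 | 4 | No | No |
| 1, 0, 3 (top answer on outlook) | 1 + 0 + 3 = 4 | No | No |
| 2, 2, 1 | 5 | Yes | Yes, if worsening is reported |

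The first participant may have started with no symptoms, and the third may have been unchanged for months. The script asks the third and not the first. The visible text has no branch for totals of 4 or less and no override for one severe answer.

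**Comparison with the drinking part of the same call.** There, the question whether the app is causing more drinking has no score gate, and the referral trigger is a rise of 3 points from baseline, which is a measure of change. Mood has no such comparison. Section 7 lists drinking, consequences, treatment-history and readiness measures at baseline, and drinking, consequences, readiness and usability measures at follow-up. Neither list contains a mood questionnaire. The self-reported worsening question is therefore the only direct check on mood change in the visible text. It needs no baseline score, so nothing requires the total to be applied first.

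**Other visible safeguards.**

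- Hotline access within the interventions (section 3) relies on the participant acting unprompted.
- So does withdrawal (section 6): "Participants are free to withdraw from participation in the study at any time upon request".
- Investigator termination (section 6) requires an exclusion criterion, and none of those listed concerns mood.
- The opening question to those who have downloaded, on how the program is working, is general.
- The ungated app-role question concerns drinking.
- The monitoring board (section 8) meets twice a year to review the project's status.

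None of these asks a participant about mood change.

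**The case against.** The strongest reply is that a severity screen followed by probing above a cut-off is an ordinary, possibly deliberate choice, and that no visible text promises to ask everyone about worsening. That stands: this is a design choice, not a contradiction. It does not remove the mismatch between a risk defined as change and a gate defined as level.

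A second reply is that parts of the appendix around the script were not available for review, and that section 3 says exacerbation procedures exist. This also stands. A reader might infer that the trial has no protection for participants whose mood worsens. The documents do not support that. They support only a statement about this branch, which is visible in full.

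A third reply is that the stop-use advice is mere permission, which participants already have through the right to withdraw. This is partly right. But being asked whether the app is adding to distress, and then told that stopping is acceptable, is a prompt that a general right does not supply.

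A reader might also size the problem by counting answers. Of the 4 × 4 × 4 = 64 possible patterns, 32 total 4 or less, which invites the inference that half of participants are missed. It does not follow. The count treats all patterns as equally likely, the items overlap in content, and a low total does not show that anyone has worsened.

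Finally, a reader might infer that lower scorers are denied the mental-health resources. That depends on the undefined label before the resource offer. If it means any positive mood answer, lower scorers with symptoms do receive them. If it means totals of 5 or more, they do not. The page layout does not settle this, and the main point does not need it.

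**Conclusion.** The point holds for the visible script: the worsening question, the app-role question and the stop-use advice are all reached only at a mood total of 5 or more out of 9. A participant who has worsened but totals 4 or less is asked neither question, even with a top answer on one item. How many participants this affects cannot be estimated from the documents.

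The conclusion assumes that the chained lines under the gate are nested as they read. Indentation may have been lost, but the worsening question refers back to the symptoms just scored, and each later step is conditional on a yes, which supports that reading. It also assumes that no procedure elsewhere covers lower scorers.

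This is a cheap safety improvement worth considering. It is not an error that threatens the trial's results.

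**What to change.** Keep the cut-off of 5 and reuse the existing wording:

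- Ask the worsening question of anyone who scores above 0 on any mood item, which includes everyone at 5 or more as now. At a total of 0 there are no symptoms to ask about.
- If the answer is yes and the participant has app or chatbot access, ask the app-role question with its stop-use branch. Delay-arm participants still waiting are not asked it.
- Offer the resources to anyone who reports worsening or gives a top answer (3) on any item, as well as to those scoring 5 or more. This also settles what the undefined label must cover at a minimum.

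**Cost.** The script edit adds branches as well as moving a question, and section 10 requires IRB approval before an amendment is used. Expect about a minute more per call and some extra resource offers to people with mild symptoms. If calls have begun, the call log should record which script was used.

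A few more participants may stop using the intervention, and only in the app and chatbot arms. Section 9 takes those who complete both surveys as the primary population, so losing these participants could unbalance the comparison. The script should therefore say that anyone advised they may stop using the app is still sent the 4-month survey.
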